8.0 Information and Risks

The devices that will transmit the data will not store any data and are FDA approved. There is therefore minimal risk. The devices are the following: Physiologic parameters of interest include pulse oximetry, temperature, blood pressure, heart rate, and weight assessed from the patient's home. Patients will be given a package that contains the following FDA-cleared devices: Nonin 3230 Bluetooth Smart Pulse Oximeters, FORA IR20 Ear Thermometer, A&D Medical Blood Pressure Monitor, and A&D Medical Weight Scale.

For the steps data, patients will be wearing a Vivofit 4. Patients will sign up on the Garmin website for the Vivofit and they will agree to the terms of use as per the Garmin company. This is noted in the consent form as per advice from the cybersecurity team. Their steps data would

not be linked to any clinical data that Garmin can capture and their terms of use will be separate from the study.

9.0 Correlative/Special Studies

No correlative studies will be performed during this study.

10.0 Study Calendar

	Baseline (T1)	Before Surgery	Treatment	Before Discharge (T2)	Day 2 Post- Discharge (T3)	Day 7 Post- Discharge (T4)	Day 14 Post- Discharge (T5)	Day 30 Post- Discharge (T6)
Informed Consent	X							
Baseline Assessment	R							
DAY OF SURGERY			X					
Post-Operative Complications – Comprehensive Complications Index (CCI) ^{131, 132}				R	R	R	R	R
Hospital Readmissions					R	R	R	R
General Symptoms - MD Anderson Symptom Inventory (MDASI) ^{55, 120}	R			R	R	R	R	R
Disease-Specific Symptoms – MDASI Symptom Library	R			R	R	R	R	R
QOL – EQ-5D-5L ^{10,113,121-125}	R			R	R	R	R	R
Semi-Structured Exit Interview/Satisfaction Tool								R
Functional Activity (daily steps taken) ¹²⁷⁻¹³⁰	Throughout study period							

X= Standard of care, R =Research

11.0 Endpoint Evaluation Criteria/Measurement of Effect

11.1 Response Criteria

Outcome Measures – Outcomes are assessed before surgery (baseline), before discharge, and until 30 days post-discharge (**Table 1**). Measures were selected based on reliability/validity, our preliminary studies, and brevity to minimize burden. ePROs will take about 4-7 minutes to complete. We will also obtain sociodemographic, clinical (diagnosis, tumor stage, neoadjuvant treatments, Charlson-Deyo co-morbidity index, time to adjuvant treatment), and surgical (Pre-op ECOG performance score, procedure, open or minimally invasive, ASA classification, date of surgery, post-op admission status and date, ICU days, post-operative events, discharge date, discharge status) data for all patients.

Table 1. Outcome Measures by Aims and Assessment Time Points

	Measures	Before Surgery (T1)	Pre-Discharge (T2)	Day 2 (T3)	Day 7 (T4)	Day 14 (T5)	Day 30 (T6)
SA 1 (Feasibility, Retention and Acceptability)	Participation Rate - % of eligible consented, reasons for non-participation, dropout and lost to follow-up rates, reasons for dropout, differential dropout by treatment arm.						Throughout study period
	Telemonitoring Completion Rate – number of PGHD and ePRO assessments completed ($\geq 70\%$)						Throughout study period
	Patient Experience – Semi-Structured Exit Interview Guide						X
SA 2 (Preliminary Efficacy)	Post-Operative Complications – Comprehensive Complications Index (CCI) ^{131, 132}		X	X	X	X	X
	Hospital Readmissions				X	X	X
	General Symptoms - MD Anderson Symptom Inventory (MDASI) ^{55, 120}	X	X	X	X	X	X
	Disease-Specific Symptoms – MDASI Symptom Library	X	X	X	X	X	X
	QOL – EQ-5D-5L ^{10,113,121-125}	X	X	X	X	X	X
	Functional Activity (daily steps taken) ¹²⁷⁻¹³⁰						Throughout study period

12.0 Data Reporting/Protocol Deviations

12.1 Data Reporting

12.1.1 Confidentiality and Storage of Records

The original data collection forms will be sent to PI and stored in a locked cabinet and office in Electronic data will be stored in encrypted, password protected, secure computers that meet all HIPAA requirements. When results of this study are reported in medical journals or at meetings, identification of those taking part will not be disclosed. Electronic health records of subjects will be securely maintained in the strictest confidence, according to current legal requirements. They will be made available for review, as required by the FDA, HHS, or other authorized users such as the NCI, under the guidelines established by the Federal Privacy Act and rules for the protection of human subjects.

12.1.2 Subject Consent Form

At the time of registration, the original signed and dated Informed Consent form, HIPAA research authorization form, and the California Experimental Subject's Bill of Rights (for the medical record) and three copies (for the subject, the research record, and the Coordinating Center) must be available. All Institutional, NCI, Federal, and State of California requirements will be fulfilled.

12.1.3 Data Collection Forms and Submission Schedule

All data will be collected from home monitoring devices, wearable devices (pedometer), and electronic PROs. Data will be sent to the location identified in Section 12.1.1 and stored in a secure location.

EQ-5D-5L - This validated tool evaluates five QOL variables: mobility, self-care, usual activities, pain/discomfort, and anxiety/depression. One final item evaluates overall health state using a visual analogue scale with the end points labeled best to worst imaginable health state (0-100 numeric value). The EQ-5D has been widely used in clinical trials and also used in quality-adjusted survival analysis.²⁴⁻²⁷

MD Anderson Symptom Inventory (MDASI) - This is a brief, validated measure of 13 common cancer-related symptoms with severity of each rated on a 10-point scale. Patients also rate how much their symptoms interfered with 6 common functional domains. The MDASI has several advantages over other symptom-assessment scales in that it applies broadly across cancer types and treatments, is easy for patients to complete, and includes items related to symptom interference with daily life. Cronbach alpha reliability ranges from 0.82 to 0.94.^{28,29}

Sociodemographic and health status – This tool covers social and demographic factors, including patient's age, sex, race/ethnicity, education, marital status, living situation, employment, income, religious preference, tobacco history, and symptoms. Patients will complete the tool at baseline.

Satisfaction Tool – This patient self-reported measure contains 13 questions designed to assess satisfaction with the electronic assessment. Data captured include: 1) ease of use of web-based surveys and wristband device; 2) Feedback on items in the web-based surveys that are distressing or difficult to comprehend; 3) Feedback on length of surveys and timing of administration; and 4) Suggestions for items that were not covered but should be added. It will be administered at the Day 30 post-discharge assessment. Both arms of the study will undergo this.

Surgical Outcomes: Comprehensive Complications Index (CCI) - The CCI® summarizes the entire patient postoperative experience with respect to complications (on a scale from 0 to 100), and is based on the established Clavien-Dindo classification. The CCI® was validated in a study with 1299 participants, and external validity was tested in a randomized trial evaluating pancreas, esophageal, and colon resections.^{31,32}

Medical Chart Audit Form and Healthcare Resource Use - Electronic health record audits will capture: 1) 30, 60, and 90 day inpatient readmissions, 2) reasons for readmissions, and 3) ER visits. The chart audits will also capture clinical (stage of disease) and surgical characteristics. If the patient seeks emergent care outside of the primary institution, the patient's permission will be obtained to review these records.

Semi-Structured Interview Guides - The semi-structured questions for exit interviews and focus groups are designed to solicit patient and surgeon/provider's perspective on the following: 1) on-boarding and setup process; 2) use of telemonitoring application for communication; 3) use and setup process of accelerometer; 4) use of telemonitoring dashboard to guide clinical care; 5) value of monitoring PROs and functional activity; 6) likes/dislikes of the program; 7) challenges and limitations of telemonitoring; and 7) suggestions on areas for improvement.

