ambulation. A critical gap in ERAS pathways is the lack of remote recovery monitoring capabilities after discharge. Perioperative care provided through ERAS pathways should also include remote monitoring and real-time interventions after hospital discharge and until full post-surgical recovery.

The current delivery model for post-discharge care and monitoring is largely inefficient, not proactive, and not cost-effective.¹² Visiting home health nurses are often dispatched for patients with unresolved acute problems (i.e. surgical wound infections, rehabilitation needs). Patients may contact the hospital when acute problems arise. This often requires hours or days to resolve, and is burdensome for patients, families, as well as the healthcare system. In critical situations, visits to the emergency room or paramedics care are accessed, either within the same healthcare system or at a different institution; these are costly and inefficient. Delays in communicating critical conditions may escalate problems beyond outpatient care. These emergency problems may also result in patients being cared for outside of the index medical system and increase cost.

The past 50 years have seen an explosion in biomedical knowledge, dramatic innovations in surgical procedures, and management of complex medical conditions, with ever more exciting clinical capabilities on the horizon. Yet, the American healthcare system is falling short on key components of quality, outcomes, and cost.¹³ The overarching imperatives for healthcare include the need to develop ways to manage its ever-increasing complexity, and curb ever-escalating costs. Opportunities now exist to address these problems; these include 1) computational power that is affordable and widely available; 2) connectivity that allows information to be accessed in real-time virtually anywhere; 3) human and organizational capabilities that improve the reliability and efficiency of care processes; 4) the recognition that effective care must be delivered in a patient-centric fashion; and 5) the recognition that, regardless of incentive structures, penalties, and payment reforms, nothing about the experiences and outcomes/value of care will improve until progress is made to revolutionize the care delivery system.^{7,13,14}

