2.2 Overview of Proposed Study

This is a pilot RCT (1:1 randomization) of a remote perioperative telemonitoring intervention in major abdominal cancer surgery. We will focus on GI malignancies, because the surgical procedures, extent of resection, and expected surgical outcomes are similar. In Aim 1, we will assess the feasibility, retention, and acceptability of the intervention through statistics of participation, intervention completion (retention) rates, and qualitative data from exit interviews. In Aim 2, surgical outcomes (post-operative complications), healthcare utilization (postoperative complications, hospital readmissions), PROs (symptoms, QOL), and functional recovery (pedometer steps) will be examined by treatment arm. Our primary endpoint is severity (grade) of postoperative complications from discharge to day 30 post-discharge. This study will be conducted in compliance with the protocol, Good Clinical Practice (GCP) and the applicable regulatory requirements.

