 - e. Blood pressure – systolic blood pressure <90 (<85 if last systolic blood pressure at discharge was <100) or >180 ; diastolic blood pressure ≥ 95 (low alert) and ≥ 100 (high alert).
 - f. Functional activity - daily steps of ≤ 1500 .
2. Patient-Reported Outcomes:
 - a. One or more symptoms rated 4 or greater (moderate-severe intensity)
 - b. One or more QOL questions rated moderate, severe, or unable to accomplish

Pathway for RN Triage and Management:

1. Patients will measure their vital signs once a day after discharge at 9 AM. Patients will have the option of measuring their vitals again at 3PM if they choose to
2. If RN identifies deviations from a priori thresholds, they will:

- i. Call the patient, and ask them to repeat all vital signs.
 - ii. Ask the patient if they are having: nausea, vomiting, fevers worsening pain, spreading redness around their incision, new or worsening drainage from their incision, chest pain, shortness of breath, difficulty breathing. Also ask if the patient is drinking at least 1.5 liters of fluid a day.
3. If vital signs on re-check are beyond threshold values but all the above patient-generated metrics are normal/negative, relay information to the on-call physician or health care provider for further determination of next course of action.
4. If vital signs on re-check are beyond threshold values and at least one of the patient-generated metrics is abnormal/positive, the patient should be evaluated within the next 24 hours. Relay information to the on-call physician or health care provider to determine exactly when/how evaluation should take place.
5. Evaluation within the next 24 hours may be:
 - i. Repeat vital signs in a pre-defined period of time to be reviewed by a health care provider
 - ii. Planned repeat phone conversation with the patient
 - iii. Clinic visit that day or the next business day
 - iv. Evaluation in the evaluation and treatment center or other urgent care/emergency department

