13.0 Statistical Considerations

13.1 Study Design

13.1.1 Sample Size Calculation and Power Analysis

We will need 128 patients (64 per arm) to detect an effect size of 0.5 in the primary outcomes as described in Aim 2 (postoperative complications, lower readmission rates, improved symptoms, QOL, and functional recovery) between the two groups, with a two-sided 0.05 significance level using a two-sample t-test and at least 80% power. We will enroll a total of 160 (80 per arm to account for an expectation of 20% attrition. Thus, we will have sufficient power for all primary outcomes, including our primary endpoint of postoperative complications.

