Similar analysis will be carried out for repeatedly measured secondary endpoints (symptom severity score, QOL). Generally speaking, we expect better scores in the intervention arm than the control arm. Healthcare resource use (e.g., hospital readmission) is a secondary endpoint. At each time point, we will estimate the ER visits/readmission rates and provide confidence intervals for each arm. Further, a binomial test for comparing two proportions will be conducted to see if there is significant difference between the readmission rates of the two arms. For simplicity, Bonferroni correction will be used both in the proportions comparisons test and the confidence intervals construction.

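### No described procedure finds readmissions and ER visits at other hospitals equally in both arms, so these events may be missed, possibly more often under usual care.

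*Combined protocol and SAP*

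**What the plan says.** Section 12.1.3 (Medical Chart Audit Form and Healthcare Resource Use) names electronic health record audit as the source for inpatient readmissions at 30, 60 and 90 days, the reasons for them, and ER visits. Outside records enter through one conditional sentence, which begins "If the patient seeks emergent care outside of the primary institution" and then provides for the patient's permission to review them.

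The background in Section 2.1 anticipates such care: "These emergency problems may also result in patients being cared for outside of the index medical system and increase cost".

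Section 13.2.1.2 sets out the analysis: "At each time point, we will estimate the ER visits/readmission rates and provide confidence intervals for each arm". A two-proportion test is then described for readmission rates, with Bonferroni correction. The same section calls healthcare resource use a secondary endpoint, although it and Section 13.1.1 also list readmission among the primary outcomes.

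In the telemonitoring arm only, Section 5.1 provides an alert pathway run by nurses. One of the four listed forms of 24-hour evaluation is "Evaluation in the evaluation and treatment center or other urgent care/emergency department".

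**The concern.** An audit of the treating centre's chart sees an outside event only if someone at the centre learns of it. The plan does not say how staff would learn, and the opportunities differ by arm. If outside events are missed equally, the observed difference shrinks. If they are missed more often under usual care, the comparison is also biased, and telemonitoring looks worse than it is.

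This matters beyond the pilot. Section 1.0 says the findings will be used to identify the effect size for a Phase III trial, and lower readmission is part of Hypothesis 2.1. A later chart review may not recover events that were never reported.

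**Working it through.** **1. Is there a route to outside events?** The Study Calendar (Section 10.0) and Table 1 (Section 11.1) schedule hospital readmissions after discharge but name no patient-reported source. Section 12.1.3 describes the EQ-5D-5L, MDASI, sociodemographic form, Satisfaction Tool and interview guides; none is described as asking about care elsewhere. The outside-records sentence covers emergent care only. The audit runs to 90 days, but the last scheduled patient contact is day 30.

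**2. Does the chance of learning of such events differ by arm?**

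| | Telemonitoring | Enhanced usual care |
|---|---|---|
| Nurse calls after alerts (5.1) | Yes | No; patients are told their data are not watched |
| Alert responses noted in the home record (13.2.1) | Possible | No alerts run |
| Day-30 exit interview (5.1) | Yes | No |
| ePRO schedule and Satisfaction Tool (5.1, 12.1.3) | Yes | Yes |
| Contacting the surgical team or call line (5.1) | Not described for this arm | Patient must initiate |

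Contact is richer in the telemonitoring arm. That makes better detection there plausible, but no document states detection by arm.

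**3. The plan's sample size.** The plan states "We will need 128 patients (64 per arm) to detect an effect size of 0.5", "with a two-sided 0.05 significance level using a two-sample t-test and at least 80% power". The exact two-sample t-test calculation gives 63.8, so 64 per arm, with power 0.801. Allowing for 20% attrition, 64 / (1 − 0.20) = 80 per arm, or 160 in total, as planned. The illustrations below use 64 per arm.

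**4. Illustration of size.** The documents give no readmission rate, ER rate, outside share or detection rate. Assumptions:
- Control event rate 33.3%. Section 1.0 says about a third of patients have a symptomatic complication that may lead to readmission. That is not a readmission rate.
- Telemonitoring rate 33.3% (no effect) or 13.3% (an assumed 20-point reduction).
- Outside share s from 10% to 40%, and probability d that an outside event is found, varied by arm.

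Observed rate = true rate × (1 − s + s × d). Example: s = 0.20 and d = 0.50 give 1 − 0.20 + 0.10 = 0.90, and 33.3% × 0.90 = 30.0%. With d = 0.90 the factor is 0.98, and 33.3% × 0.98 = 32.7%.

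Power is for a two-sided 0.05 comparison of two proportions without the Bonferroni correction. Differences are control minus telemonitoring.

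| True rates, control / tele | s | d, control / tele | Observed, control / tele | Difference (points) | Power |
|---|---|---|---|---|---|
| 33.3 / 33.3 | 20% | 50 / 50% | 30.0 / 30.0% | 0 | – |
| 33.3 / 33.3 | 20% | 50 / 90% | 30.0 / 32.7% | −2.7 | – |
| 33.3 / 33.3 | 40% | 50 / 90% | 26.7 / 32.0% | −5.3 | – |
| 33.3 / 33.3 | 20% | 0 / 100% | 26.7 / 33.3% | −6.7 | – |
| 33.3 / 13.3 | none missed | – | 33.3 / 13.3% | 20.0 | 0.77 |
| 33.3 / 13.3 | 20% | 50 / 50% | 30.0 / 12.0% | 18.0 | 0.71 |
| 33.3 / 13.3 | 10% | 50 / 90% | 31.7 / 13.2% | 18.5 | 0.71 |
| 33.3 / 13.3 | 20% | 50 / 90% | 30.0 / 13.0% | 17.0 | 0.65 |
| 33.3 / 13.3 | 40% | 50 / 90% | 26.7 / 12.8% | 13.9 | 0.51 |
| 33.3 / 13.3 | 20% | 90 / 50% | 32.7 / 12.0% | 20.7 | 0.81 |

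Equal detection dilutes a real difference and creates none where there is none. Lower detection in the control arm works against telemonitoring; the reverse pattern favours it.

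**5. Visits directed by the pathway.** The ER counts are not split by whether the nurse pathway directed the visit. Section 13.2.1 does store care actions that follow alerts, including scheduled visits, and lets nurses document alert responses in the home record. Directed visits can therefore be traced from data already planned.

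**The case against.** The plan does provide for outside emergent-care records, and control patients are not out of reach. They follow the same ePRO schedule and are told to call with problems, and Section 5.5 has staff review responses to all outcome measures without limiting this to one arm. Section 12.1.2 requires a HIPAA research authorization at registration, and the consent pages are not in the available copy, so it cannot be said that an outside-records release is missing. All of this stands. It narrows the point, but it supplies no question about care elsewhere.

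A reader might infer more in three ways that the documents do not support.

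- **That the flaws must all work against telemonitoring.** Section 2.1 says problems may lead to outside care and gives no frequency. Detection by arm is not given either, so the direction is an inference from the contact schedule.
- **That counting pathway-directed ER visits is an error.** They are a consequence of assignment and belong in total utilization by randomized arm. Some may replace visits the patient would have made anyway. The pathway lists no inpatient admission, whereas the planned test is described for readmission.
- **That the pilot's 34% alert rate (Section 2.4) sizes the directed visits.** That is a first-week rate for patient-reported outcomes, with a different QOL threshold. The Section 5.1 pathway escalates on re-checked vital signs, so the rate does not transfer.

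**Conclusion.** The ascertainment gap holds. As described, the plan has no systematic way, applied equally to both arms, to find readmissions and ER visits at other hospitals. Staff contact that could reveal them is richer under telemonitoring, so selective loss in the control arm is plausible but not shown.

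In the assumed scenarios with no true effect, better detection under telemonitoring creates a false difference of 2.7 to 6.7 points against it. With a true 20-point reduction, equal 50% detection at a 20% outside share costs 2 points, and 50% versus 90% detection costs 1.5 to 6.1 points as the outside share goes from 10% to 40%. Every one of these figures rests on assumed event, outside-care and detection rates.

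The single primary endpoint, complication severity, is not the subject here. This is an inexpensive improvement to a secondary endpoint whose estimate is meant to inform the Phase III design.

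**What to change.** 1. Add one identical item to the ePRO set in both arms at days 7, 14 and 30: *Since your last survey, have you been to any emergency room or admitted to any hospital? Where and when?* The day 7 version should ask about the time since discharge, because the day 2 survey would not carry the item. Report item completion by arm.
2. Confirm that the authorization signed at registration covers records from other hospitals, and amend it if it does not.
3. Make 30-day utilization the between-arm comparison. Label the 60- and 90-day figures as chart-audit only unless the item is also sent at those times.
4. Keep all-cause counts by randomized arm as the main analysis.
5. As description only, use the planned alert-response data to report how many telemonitoring-arm ER visits the nurse pathway directed. Do not compare arms after removing them: control patients who call the surgical team or hospital line may also be sent to an ER by staff, and those visits would remain.

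The cost is slightly longer surveys, some outside-record requests, and possibly an edit to the authorization form. The item depends on survey completion, so it reduces the gap but does not close it.
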